#### Amendments

Any amendments or administrative changes to the IRB approved protocol will not be initiated without submission of an amendment for IRB review and approval.

Any amendment to the protocol that significantly affects the safety of subjects, the scope of the investigation, or the scientific quality of the study are required to submit the amendment for FDA review.

#### Annual Reports

An annual progress report will be submitted to the FDA within 60 days of the anniversary of the date that the IND went into effect (21 CFR 312.33)

#### Informed Consent

Informed consent is required because all eligible subjects are at least 18 years old. Subjects who are capable of giving consent and who are alert and competent, will be asked, following an appropriate discussion of risks and benefits, to give consent to the study. For those with diminished mental capacity, a Legal Authorized Representative will be used.

#### Potential Risks

Loss of confidentiality of the subject is a potential risk of the study; however, safeguards are in place to protect against this. There is an additional medical risk of rash around the injection site if randomized to pAF treatment.

#### Protection Against Potential Risks

Regarding loss/breach of privacy and confidentiality, all applicable parties (e.g. clinical sites, DCC) will be responsible for ensuring that appropriate data security procedures are in place.

#### Potential Benefits

There may be a potential benefit in helping decrease the size of wounds that are treated with pAF and the amount of time it takes to decrease the wound size.

## **11 - REGULATORY CONSIDERATIONS**

#### Food and Drug Administration

This trial is being conducted under an Investigational New Drug application. The clinical investigator at each participating site will complete a Form FDA 1572, "Statement of Investigator."

#### Health Insurance Portability and Accountability Act

Data elements collected include the date of birth and date of visits. Prior to statistical analyses, dates will be used to calculate patient age at the time of the study events. The final data sets (used for study analyses and made available at the end of the study) will be de-identified, and will exclude these specific dates.

Data elements for race, ethnicity, and gender are also being collected. These demographic data are required for Federal reporting purposes to delineate subject accrual by race, ethnicity, and gender.

### Inclusion of Women and Minorities

There will be no exclusion of patients based on gender, race, or ethnicity.

## **12- DATA COORDINATING CENTER**

### Overview

The Data Coordinating Center (DCC) in the Department of Pediatrics at the University Of Utah School Of Medicine provides data coordination and management services for a variety of national research networks. Anchoring these services is a new state-of-the art, energy efficient data center. The data center facility supports more than 3500 users around the country and provides a secure, reliable, enterprise-wide infrastructure for delivering mission critical DCC systems and services.

### Facility, Hardware, Storage, Data Backup and System Availability

The data center was built using high industry standards and energy efficient cooling solutions. The data center is cooled by a LCP (Liquid Cooling Package) inline cooling technology; providing efficiency, redundancy and the modularity required. Cooling is based upon a hot/cold aisle design that allows for even air distribution with minimal hot spots. The data center electrical power system contains an uninterruptible power system (UPS) with a diesel backup generator. The data center is protected with a FM200 fire suppression system to act as a secondary system to the smoke detectors. The data center provides enhanced security to safeguard the equipment and the data within it. Entry into the data center is restricted by card access and layered security measures and controls. The data center and external building access points are monitored with video surveillance.

The data center has a virtualized environment. The virtualized environment consists of more than 400 virtual servers and nearly 25 physical servers. The data center's virtualized solution provides key advantages; 1) high availability – in the event of hardware failure, virtual servers automatically go back online in a seamless process. 2) Flexible infrastructure – disk storage, memory and processor capacity can be increased or reallocated at any time. 3) Rapid deployment – servers can be provisioned on demand.

Production servers running mission critical applications are clustered and configured for failover events. Servers are backed up with encryption through a dedicated backup server. Our storage area networking (SAN) applications, clusters, and switch-to-switch links are on a 10 gigabit network. Incremental backups occur Monday through Friday. A full system backup occurs weekly. Full backups are taken off site on a weekly basis to an off-site commercial storage facility. The data center currently manages over 150 terabytes of data.

Our information systems are available 24 hours a day, 7 days a week to all users, unless a scheduled maintenance interruption or mitigation of an unexpected event is required. If this occurs, we notify all users of the relevant systems, and data entry can be deferred until after the interruption is over.

### Security, Support Encryption and Confidentiality

The data center coordinates the network infrastructure and security with the University Information Technology (UIT) at the University of Utah. This provides us with effective firewall hardware, automatic network intrusion detection, and the expertise of dedicated security experts working at the University. Centralized authentication and communication over public networks is encrypted using transport layer security (TLS) or virtual private network (VPN) technologies, both of which provide at least 128 bit encryption.

All network traffic is monitored for intrusion attempts, security scans are regularly run against our servers, and our IT staff are notified of intrusion alerts. Security is maintained with Windows user/group domain-level security. Users are required to change their passwords every 90 days. All files are protected at user/group levels; database security is handled in a similar manner with group-level access to databases, tables, and views in Microsoft SQL Server. Finally, all laptop computers in use in the DCC are whole-disk encrypted.

The data center uses control center tools to continuously monitor systems and failure alerts. Environmental and network systems are also monitored to ensure up time. And highly trained system administrators on staff are available to respond in high risk emergency events.

All personnel involved with the DCC have signed confidentiality agreements concerning data encountered in the course of their daily work. All personnel (including administrative staff) have received Human Subjects Protection and Health Information Portability and Accountability Act (HIPAA) education. We require all users to sign specific agreements concerning security, confidentiality, and use of our information systems, before access is provided.

#### Record Access

The medical record and study files (including informed consent) must be made available to authorized representatives of the Data Coordinating Center, upon request, for source verification of study documentation. In addition, medical information and data generated by this study must be available for inspection upon request by representatives (when applicable) of the Food and Drug Administration (FDA), NIH, other Federal funders, and the Institutional Review Board (IRB) for each study site.

1 PREFACE

1.1 Purpose of SAP

This Statistical Analysis Plan (SAP) describes the planned analysis and reporting for the protocol: A Phase I/II Clinical Trial to Determine Safety and Feasibility of Using an Acellular Amniotic Fluid Application to Expedite Healing in Chronic Wounds.

The structure and content of this SAP provides sufficient detail to meet the requirements and standards set by the Data Coordinating Center (DCC).

1.2 Auxiliary/Other Documents

The following documents were reviewed in preparation of this SAP:

- Protocol (including intended revisions): A Phase I/II Clinical Trial to Determine Safety and Feasibility of Using an Acellular Amniotic Fluid Application to Expedite Healing in Chronic Wounds
- Case Report Forms (CRFs) for the pAF for the Treatment of Chronic Wounds protocol

The reader of this SAP is encouraged to read the protocol for details on the conduct of this study, and the operational aspects of clinical assessments.

The purpose of this SAP is to outline the planned analyses to be completed for the pAF for the Treatment of Chronic Wounds trial. The planned analyses identified in this SAP will be included in future study abstracts and manuscripts. Also, exploratory analyses not necessarily identified in this SAP may be performed. Any post hoc, or unplanned, analyses not explicitly identified in this SAP will be clearly identified as such in any published reports from this study.

It is possible that, due to updates or identification of errors in specific statistical software discussed in this SAP, the exact technical specifications for carrying out a given analysis may be modified. This is considered acceptable as long as the original, prespecified statistical analytic approach is completely followed in the revised technical specifications.

2 STUDY OBJECTIVES AND OUTCOMES

2.1 Study Objectives

2.1.1 Primary Objective

The primary objective of the pAF for the Treatment of Chronic Wounds trial is:

1. To determine the safety of using processed amniotic fluid (pAF) to treat patients with chronic wounds.

2.1.2 Secondary Objective

The secondary objective of the pAF for the Treatment of Chronic Wounds trial is:

1. To determine efficacy by examining a reduction in wound size after application of pAF compared to Standard of Care (SOC).

2.2 Study Outcomes

2.2.1 Primary Outcome

There is one primary outcome, which pertains to safety: whether or not the subject has any post-randomization serious adverse events (SAEs) related to study treatment up to and including the final visit (Visit 5).

Eligibility for Primary Analysis The primary outcome is to be evaluated in subjects who are randomized. Randomization does not occur until Visit 2 to make sure a wound is not randomized if the subject has become ineligible between Visit 1 and Visit 2. The inclusion/exclusion criteria from baseline should be reevaluated as feasible (without needing to perform additional lab tests). A wound is also considered ineligible for randomization if it has reduced in area by at least 50% with standard of care since Visit 1. To permit an efficient eligibility assessment work-flow at Visit 2, clinician judgment may be used to ascertain if the wound has reduced in area by at least 50% since Visit 1.

2.2.2 Secondary Outcome

The secondary outcome pertains to efficacy: the percentage reduction in wound area at Visit 5 relative to Visit 2.

Eligibility for Secondary Analysis The secondary outcome is to be evaluated in subjects who are randomized.

2.2.3 Exploratory Outcome(s)

Exploratory outcomes include:

- Wound closure at Visit 5
- Wound recurrence at Visit 5
- Percent reduction in wound area at Visits 3, 4 (relative to Visit 2)
- Percent reduction in maximal wound depth at Visits 3, 4, 5 (relative to Visit 2)
- Change in wound-associated pain at Visits 3, 4, 5 (relative to Visit 2)
- Hypertrophic scar formation at Visit 5 (graded with modified Vancouver Scar Scale)
- Wound infection at Visit 4 (per wound culture exceeding the threshold)

Eligibility for Prespecified Exploratory Analyses The prespecified exploratory outcomes are to be evaluated in subjects who are randomized. Recurrence of wounds at Visit 5 will be assessed only in subjects with wound closure prior to Visit 5. It is possible that additional exploratory analyses will be conducted, and such analyses may have different eligibility criteria.

2.2.4 Safety Outcome(s)

The primary outcome of this study is related to safety: the occurrence of any post-randomization SAEs related to study participation, up to and including the final visit. In addition, other safety outcomes evaluated (from randomization up to and including the final visit) include the following:

- Occurrence of any post-randomization SAEs (regardless of relatedness to study participation)
- Occurrence of any post-randomization adverse events (AEs)
- Occurrence of any post-randomization AEs related to study participation
- Occurrence of any post-randomization unexpected AEs

3 STUDY DESIGN AND METHODS

3.1 Overall Study Design

The pAF Wound trial is a two-arm, randomized controlled trial to assess the safety and efficacy of using processed amniotic fluid (pAF) to treat chronic wounds. The largest qualifying wound per subject will be assessed at the initial visit. At Visit 2 (about 6 weeks later), if the

wound has not decreased by at least 50% in area, the patient's wound is to be randomized to either standard of care or the injection of pAF. The randomized treatment is given to the randomized wound at Visit 2 and at Visit 3 (about six weeks after Visit 2). Thereafter, two additional visits (Visit 4 about six weeks after Visit 3, Visit 5 about 3 months after Visit 4) are used to collect further information. At all study visits, non-randomized wounds are to receive standard of care treatment.

3.2 Method of Treatment Assignment and Randomization

Subjects will be randomized into two groups at a 1:1 ratio. The randomization will employ random block sizes of two, four, or six subjects to limit the ability to predict the next subject's treatment prior to randomization. It is not guaranteed that exactly 30 subjects will be randomized to each arm due to random block sizes and the unlikely event of administering backup randomization for a subject. There may be as few as 28 in the pAF arm (32 in the standard of care–SOC–arm) or as many as 32 in the pAF arm (28 in the SOC arm). Because of the small number of overall patients and the anticipated slow accrual rate, stratification by subject characteristics will not be used in the randomization procedure.

3.2.1 Delivery of Randomization and Emergency Backup

The randomization treatment assignment will be generated by a DCC faculty statistician and uploaded to a REDCap instance. At Visit 2, if a subject is still eligible to have the largest qualifying wound randomized to treatment, the treatment assignment will be delivered using the randomization module in REDCap. Backup randomization envelopes will be available to the research coordinator(s) and/or other authorized study staff, to be used only when technical difficulties preclude use of the web-based randomization.

3.2.2 Handling of Incorrect Randomization in Study Analyses and Reports

The Intention-to-Treat (ITT) principle will be used, in that subjects will be analyzed in the arm to which they were randomized. Assuming that misrandomization is infrequent, no further adjustments are planned for misrandomizations beyond applying the ITT principle.

3.3 Treatment Masking (Blinding)

This is an unblinded trial, but the person interacting with the imaging software is to be blinded to treatment arm to avoid bias between arms for purposes of measuring the secondary outcome. This is because wound area calculations used by the software rely on an individual manually outlining the wound within the imaging software.

3.4 Study Intervention Compliance

As part of the work-flow for assessments at Visits 2–5, the subject will be asked if any investigational wound care has been received since the last study visit that is external to that described in the protocol. Subjects who received investigational wound care between Visits 1 and 2 are not to be randomized as the protocol does not allow such individuals to receive any pAF injections during the study. Subjects randomized to the pAF arm who receive external wound care between Visits 2 and 3 are not eligible to receive pAF at Visit 3. Follow-up data at Visits 2–5 should still be collected on all individuals who were randomized to a treatment arm at Visit 2, regardless of study intervention compliance. The only exceptions to the desire to follow-up are for individuals who die or formally withdraw during the study.

4 STUDY SUBJECTS AND ANALYSIS POPULATIONS

4.1 Eligibility

The inclusion and exclusion criteria for the pAF for the Treatment of Chronic Wounds Trial are described in the protocol. Enrolled subjects may be randomized to a treatment arm at Visit 2 if still eligible and if the wound area has not decreased by $\geq 50\%$ since Visit 1. The determination of whether the wound has decreased by $\geq 50\%$ since Visit 1 may be per the rectangular approximation to the area at Visit 1 and at Visit 2 or per clinician assessment, even if subsequent analysis (i.e., wound size per the imaging software) would yield a different conclusion.

4.2 Populations for Analyses

4.2.1 Eligible and Approached for Consent Population

The CONSORT-like diagram will begin with its most general population being those who met all eligibility criteria and who were approached for consent by study staff.

4.2.2 Enrolled Population

All subjects who meet all inclusion criteria, none of the exclusion criteria, have the appropriate consent, and are enrolled into the trial at Visit 1 will be considered part of the enrolled population. That is, the enrolled population consists of the subset of the eligible and approached population who provide consent and are enrolled into the trial at Visit 1.

4.2.3 Intention-to-Treat Population

The Intention-to-Treat (ITT) population consists of all enrolled subjects who at Visit 2 are randomized to have the study wound be treated with pAF or SOC.

In order to be randomized, the wound area must not have decreased by at least 50% at Visit 2 relative to Visit 1. Because of the infeasibility of having adjudication of imaging-software-derived wound areas in real time at Visit 2, the rectangular approximation to the wound area and/or clinician judgment will be used for the Visit 1 and Visit 2 areas to determine if the Visit 2 wound area is more than half of the Visit 1 wound area. Furthermore, the study inclusion/exclusion criteria are to be reassessed at Visit 2 to ensure the subject is still eligible for the study. Receiving investigational treatment to the wound outside of the study between Visits 1 and 2 render the subject ineligible to be randomized.

Even if a $\geq 50\%$ reduction in wound size by Visit 2 causes the subject to be ineligible for randomization of one wound to pAF/SOC, the subject will still be considered part of the enrolled population. Likewise, even if a subject is not randomized because, e.g., out-of-study investigational wound care was received after Visit 1 and before Visit 2, the subject is still considered part of the enrolled population.

There is no requirement that the subject receive the randomized treatment (e.g., that pAF be injected into the wound of somebody randomized to the pAF treatment arm) to be part of this population. Primary and secondary analyses (and exploratory analyses, unless explicitly noted otherwise) comparing the arms are to be performed according to the arm to which the subject was randomized, even if this differs from the actual treatment received.

4.2.4 Per-Protocol Efficacy Population

The Per-protocol (PP) population consists of all subjects from the ITT population who meet both of the following conditions:

- The subject did not receive out-of-study investigational wound care between enrollment and the earlier of Visit 5 and the time when Visit 5 should have occurred; and
- The subject received the randomized treatment at Visit 2 and, if applicable, at Visit 3. Treatment at Visit 3 is applicable unless the wound was healed at the time when Visit 3 was to have occurred or the subject had a study-related SAE by the time of Visit 3 that precluded treatment administration. Study-related is defined as having a classification of “probably related” or “possibly related.”

4.2.5 Closed Wound Efficacy Populations

Several analyses are only applicable among those whose wound closes between Visits 2 and 5. The closed wound at Visit 3 (CW3) population consists of all subjects from the ITT

population whose wound is closed at Visit 3. The closed wound at Visit 4 (CW4) and closed wound at Visit 5 (CW5) populations are analogously defined.

4.2.6 Safety Population

The safety population (SAFETY) coincides with the ITT population. The SAFETY population admits comparisons between arms.

An additional population for assessing safety will be limited to ITT participants randomized to the pAF treatment arm who received at least one pAF injection during the course of the study.

5 GENERAL ISSUES FOR STATISTICAL ANALYSES

5.1 Analysis Software

Analysis will be performed using SAS® Software version 9.4 or later whenever possible. Other software packages, including R and StatXact®, may be used for particular specialized procedures. IVEware is the preferred software for creating the study's multiply imputed data sets.

5.2 Methods for Withdrawals, Missing Data, and Outliers

The applicability of some measures will depend on whether or not the wound is (or has previously) closed. Values that are not observed because they are not applicable will be excluded from the pertinent analyses, rather than regarded as missing. Values that are not directly obtained but are implied by other measurements will use the implied value.

Multiple imputation (MI) will be applied for analyses of the secondary outcome. Using MI leverages partial information and attempts to reduce bias in final inferences that could result from a naive complete-case analysis. A minimum of ten data sets will be generated. Chained equations will be used along with variable selection; for imputing missing values for a given variable, the input variables will be limited to those that increase the R^2 value by at least 0.01. If feasible, MI will be conducted separately within each treatment arm. The pool of variables for the imputation process includes: wound area per the imaging software at Visits 1, 2, 3, 4, and 5; treatment arm if infeasible to impute by treatment arm; and indicators for comorbidities. The following comorbidities will be considered: diabetes, peripheral vascular disease, and immunosuppression. Imputation will exclude individuals

who were not randomized.

Visit measurements obtained outside the permissible window may or may not be used in the imputation model. We will determine the closest visit number to assign the out-of-window visit per the protocol's timing for follow-up visits. The out-of-window measurement will be used for the determined visit number in the case that the visit number does not already have a valid measurement (and if there are multiple out-of-window candidate measurements, the one closest to the protocol timing will be used). Otherwise, the out-of-window measurement will be ignored.

Multiple imputation may also be used for exploratory outcomes, as appropriate.

We do not plan to use different methods for missing data due to withdrawal compared with data missing for other reasons.

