5.3 Multiple Comparisons and Multiplicity

There is one primary endpoint (occurrence of post-randomization study-related SAEs on or before Visit 5), which is not intended to be tested between arms. Instead, descriptive summaries and confidence intervals will be constructed by study arm. There is one secondary endpoint (percent reduction in wound area at Visit 5 compared to Visit 2), which will be tested at $\alpha = 0.05$. The additional analyses are regarded as exploratory and therefore no adjustments are indicated for the multiplicity of testing; each will use $\alpha = 0.05$.

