5.6 Independent Review

All statistical analyses for primary reporting of trial results will be independently verified through dual programming. Two statisticians will each program all datasets and analyses for the DSMB reports and the primary manuscript(s) and the results will be compared. This process will begin at the analysis design stage and will continue through writing of abstracts and manuscripts for primary analyses.

Additional analyses for secondary abstracts or manuscripts will use a second statistician conducting at least code review, if not dual programming.

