7.3 Secondary Outcome Analysis

The secondary outcome is the percentage reduction in wound area at Visit 5 relative to wound area at Visit 2. Because reduction in wound area at Visits 3 and 4 are exploratory outcomes, the general definition for deriving percent reduction in wound area at Visit k relative to Visit 2 is

$$1 - \frac{\text{Visit } k \text{ wound area}}{\text{Visit 2 wound area}} \times 100\%,$$

with all measurements expressed as the area determined through the imaging software. Wound area will be reported in (cm^2), although for purposes of the percent reduction the units are immaterial. The percent reductions will be summarized overall and by assigned treatment arm for the ITT population, using means and standard deviations or medians and interquartile ranges, as appropriate given the observed skewness and presence of extreme outliers.

The inclusion criteria limit the study to wounds which are difficult to heal, explaining why patients are not randomized if the wound area shrinks significantly between Visits 1 and 2. Therefore, any greater reduction in wound size with pAF than with SOC will suggest efficacy of pAF for wound treatment. To describe a trend in a statistical hypothesis testing framework, the following two-sided hypothesis will be assessed:

$$H_0 : \mu_{pAF} = \mu_{SOC} \text{ versus } H_1 : \mu_{pAF} \neq \mu_{SOC}.$$

Note that μ_{pAF} (μ_{SOC}) represents the average percent reduction in wound area at Visit 5 compared to Visit 2 for the pAF (SOC) treatment.

To provide an intuitive effect size, percentage change from Visit 2 will be computed at Visits 3, 4, and 5 (approximately 6, 12, and 25 weeks after randomization). If there are study visits outside of the visit's ± 1 week window, all percentages will be divided by the number of elapsed days since Visit 2, so the outcome is expressed as a percentage change per day.

If the change in wound size at Visit 5 follows a reasonably symmetric distribution within each treatment arm, then a two-sided, two-sample, unpooled t-test will be performed to compare the mean percentage reductions at Visit 5 between arms for the ITT population. If the distribution is very asymmetrical in one or both arms, a Wilcoxon rank sum test will be used. In either case, Rubin's rules will be used to combine inferences across the multiply imputed data sets and the test will be declared statistically significant if the two-sided p-value is ≤ 0.05 .

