7.3.1 Additional Analyses of Secondary Outcome

The primary analysis of the secondary outcome explicitly adopts a multiple imputation approach. Two sensitivity analyses will be conducted in which missing values are replaced with the lowest (highest) observed value in the assigned treatment arm.

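### SAP 5.2 lets the secondary efficacy test rest on ten imputed data sets; at the SAP's assumed effect with an assumed 20% missing, two runs on the same data give opposite verdicts in about 3–9% of trials, against about 1–2.5% with 100.

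*SAP*

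**What the plan says.** SAP 7.3.1 makes multiple imputation the main analysis of the percent reduction in wound area at Visit 5: "The primary analysis of the secondary outcome explicitly adopts a multiple imputation approach". SAP 5.2 specifies chained equations with variable selection, and adds "If feasible, MI will be conducted separately within each treatment arm". On the number of imputations it says only "A minimum of ten data sets will be generated". It gives no target, no rule that raises the number with the amount of missing data, and no limit on Monte Carlo error.

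Under SAP 7.3 the test is an unpooled t-test or a Wilcoxon rank sum test, depending on symmetry. For both tests the SAP says that "Rubin's rules will be used to combine inferences across the multiply imputed data sets". A pooled two-sided p of 0.05 or less then counts as significant. SAP 5.3 names this as the one secondary endpoint, tested at 0.05.

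SAP 5.6 requires dual programming: "Two statisticians will each program all datasets and analyses for the DSMB reports and the primary manuscript(s) and the results will be compared". It does not say whether the two programmers share imputed data sets. Neither document states a random seed or an expected rate of missing Visit 5 areas. The power figure in SAP 8 assumes none are missing.

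**The concern.** A pooled p-value from a finite number of imputations depends on the data and also on the random draws. With many imputations the second part is negligible. With ten, and 30 subjects per arm, it may not be. The plan then applies a fixed cut at 0.05 to a number that would change if the same program were run again. For a result near the cut, the verdict could turn on the draws.

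Dual programming raises a related practical point. Two correct programs that impute separately will give different pooled p-values. The SAP does not say how to tell that difference from a coding error, or which p-value to report.

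**Working it through.** **Inputs from the documents.** 30 per arm. The reduction is 100% with probability 0.5 (pAF) or 0.2 (SOC), and otherwise uniform on 0–100% (SAP 8). Two-sided 0.05, unpooled t or rank sum, Rubin's rules (SAP 7.3). Imputation by arm (SAP 5.2). Number of imputations m = 10, the permitted minimum.

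**Assumptions, not in the documents.** The share of Visit 5 areas missing (5–30%), missing completely at random. The correlation rho between Visit 5 and one earlier-visit predictor (0–0.9). Whether imputed reductions are capped at 100%.

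**Step 1, the plan's own figure.** With no missing data, 100,000 simulated trials give rank-sum power of 54.5% without and 54.1% with continuity correction. SAP 8 states about 54%, so the planning scenario reproduces.

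**Step 2, why m matters.** Rubin's total variance is T = U + (1 + 1/m)B, with U the within- and B the between-imputation variance. Given the data, the pooled estimate has Monte Carlo variance B/m. With λ = (1 + 1/m)B/T, the Monte Carlo SD of the test statistic is about s = √(λ/(m+1)). At rho 0.7, 20% missing, capped, Welch, the simulation gave λ = 0.12 at m = 10 and 0.11 at m = 100:

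- m = 10: s = √(0.12/11) = 0.104
- m = 100: s = √(0.11/101) = 0.033

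Two runs differ by 2s/√π on average. The chance that they straddle the cut is about that distance times the density of the statistic at the cut. At the SAP effect the power in this setting is about 36%, which puts the density near 0.373:

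- m = 10: 0.373 × 1.128 × 0.104 = 4.4% (simulated 5.0%)
- m = 100: 0.373 × 1.128 × 0.033 = 1.4% (simulated 1.3%)
- no effect, m = 10: density in two tails 2 × 0.0584 = 0.117, so 0.117 × 1.128 × 0.104 = 1.4% (simulated 1.6%)

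The formula ignores run-to-run variation in T, so it runs a little low at m = 10. It shows why the rate depends on the true effect.

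**Step 3, simulation.** Each trial was imputed twice with independent draws (Bayesian normal regression by arm), and opposite verdicts were counted. Most cells have 4,000–6,000 trials. At 5% and 6,000 trials the standard error is √(0.05 × 0.95/6,000) = 0.3 percentage points.

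20% missing, SAP effect, m = 10, capped:

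| rho | Welch | Rank sum |
|---|---|---|
| 0 | 6.8% | 6.7% |
| 0.5 | 5.7% | 5.7% |
| 0.7 | 5.0% | 5.5% |
| 0.85 | 3.7% | 4.5% |
| 0.9 | 3.4% | 3.4% |

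Other settings (both tests unless stated):

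| Setting | m = 10 | m = 100 |
|---|---|---|
| 20% missing, capped, rho 0–0.9 | 3.4–6.8% | 1.1–2.1% |
| 20% missing, uncapped, rho 0–0.85 | 4.7–8.6% | 1.4–2.5% |
| 5% missing, capped, rho 0.7 | 2.5–2.8% | not run |
| 10% missing, capped, rho 0.7 | 3.1–3.3% | not run |
| 10% missing, uncapped, rho 0.7 | 3.9–4.7% | not run |
| 30% missing, rho 0.7 | 6.9–8.1% | 2.2% (Welch, capped) |
| 20% missing, half the effect (0.35 v 0.2), capped | 3.0–3.3% | not run |
| 20% missing, no effect | 0.8–2.1% | not run |

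At 30% missing with m = 100 (Welch, capped), the rate is 2.6% at rho 0 and 1.5% at rho 0.9.

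**Step 4, results near the cut.** At the SAP effect with 20% missing, about 15% of trials have a first p between 0.03 and 0.08. Among these, roughly a quarter change verdict on a second run at m = 10 (22–32% across settings), against about 7–12% at m = 100.

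**The case against.** The strongest reply is that ten is a floor. The statisticians may raise it once they see how much is missing, and the rates above describe the least that the plan permits. That is true. It limits the finding to what the SAP allows, and if a larger number is intended, stating it costs nothing.

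A second reply is that little hangs on the result. SAP 7.3 presents the test as describing a trend. SAP 8 rests the move to the next phase on study-related SAEs in the pAF arm and leaves efficacy to a later, adequately powered trial. SAP 7.3.1 also adds lowest- and highest-value sensitivity analyses that need no random draws. This stands, and it makes the point a minor one.

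Third, the simulation uses at most one earlier visit, whereas SAP 5.2 offers all the visit areas and three comorbidities as predictors. Better prediction lowers the rate, which is why rho is shown up to 0.9. The t-test and rank sum test give similar answers.

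A reader might go further in three ways that the documents do not support:

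- That a larger m would make the two programmers' results match. It would not: 100 separate draws also differ. A common seed does not by itself make two independently written programs agree either. Only shared imputed data do, and SAP 5.6 neither requires nor forbids sharing.
- That no seed exists anywhere. SAP 5.5 refers to a separate dataset specifications document, which was not available, and a seed could be recorded there.
- That the open seed would be chosen to suit the result. DCC biostatisticians do see arm-level data in closed session (SAP 6.4), but nothing suggests such use. The gap is one of prespecification only.

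**Conclusion.** The point holds as a small, avoidable source of noise in the only efficacy test to which SAP 5.3 gives secondary-endpoint status. Its size is conditional. At the SAP's planning effect and 20% missing, two runs disagree in about 3–9% of trials at m = 10, depending on how well earlier visits predict Visit 5 and whether imputations are capped, against about 1–2.5% at m = 100. At m = 10 the rate is about 2.5–4% with 5–10% missing (4.7% in one uncapped rank-sum setting). It is about 5–8% with 30% missing, where m = 100 gives about 1.5–2.6%. With 20% missing and no effect it is about 1–2%.

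It would be wrong to read any one of these as a general failure rate of the plan. The missing rate, its randomness and the correlation between visits are all assumed, and most trials are far enough from 0.05 to be unaffected. Nor is this a confirmatory result on which a decision turns. The case for change is that the gain costs almost nothing.

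**What to change.** In SAP 5.2, replace the floor of ten with at least 100 imputed data sets for the secondary outcome. State that they are generated once, with a seed recorded in the SAP or the dataset specifications before database lock, and that both programmers use that one set for the comparison in SAP 5.6. Because SAP 5.6 has each statistician program all datasets, the sentence should say that the imputed data are shared by design. The second programmer then verifies the imputation code and programs the pooled test independently.

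The protocol needs no change, since its statistical section defers imputation details to the SAP. The cost is one sentence and minutes of computing time for 60 subjects. The outcome, test, significance level and trial conduct stay as they are. Some noise remains at m = 100 for results very close to 0.05, but the recorded seed and shared data fix which result is reported.
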